## Scientific Background

Previous BRITE study:

In a previous study, [name] and colleagues developed a brief, inpatient- based, novel intervention with an accompanying safety planning app (BRITE) for psychiatrically hospitalized, suicidal adolescents. In a pilot RCT with 66 adolescents, this app-supported intervention cut the incidence of recurrent suicide attempts by half (Incidence rate ratio [IRR] for attempts=0.47, 95%CI 0.12-1.56, p=0.18), with a stronger effect in the 80% of adolescents with a previous history of a suicide attempt (IRR=0.23, 95% CI, 0.05-1.09). The app was accessed an average of 29 times over a 6-month period, 45.5% accessed the safety plan, and the more frequently the app was used, the greater the decline in suicidal ideation and increase in reasons for living ( $\rho=0.36$ ,  $p=0.08$ ). Participants rated BRITE high on usability using the Post-Study Satisfaction and Usability Questionnaire (lower score indicates greater satisfaction, range 10-70, mean scores 17.6-18.4). Moreover, clinicians who implanted the interventions wanted the app to guide them in formulating the safety plan and populating the app for use by the adolescent. These data provide preliminary support for the clinical utility of an app-supported intervention to reduce suicide risk in adolescents. While a multitude of apps are freely available on the Apple App store and Google Play Store, this is the only app available to promote self management of distress and suicidal ideation that has undergone a clinical trial with published results. We have made the app available for clinicians to use as part of their clinical care to aid their patients with self management of mood dysregulation and suicidality.

We are currently also disseminating the BRITEPath intervention for clinical use (STUDY20050047) and collecting anonymous usability feedback in real world clinical settings to further develop BRITE for future research and non-research projects, ultimately providing this in a much wider fashion for clinical use. In the currently approved BRITEPath related studies (STUDY18120080, STUDY20010135 & STUDY19050132) we developed a virtual treatment manual designed to guide clinicians in delivering the intervention and a clinician dashboard to monitor symptoms and treatment progress. It is this version that gained attention from clinicians which are providing for clinical use and would like to collect anonymized user data already collected through the clinician training process and on the app and clinician dashboard. We will not collect any clinical data from patients or clinicians as part of their clinical care.

Adolescent suicide is the second-leading cause of mortality in adolescents, and adolescent suicidal behavior is a common cause of morbidity associated with significant functional impairment. The rates of both adolescent suicide and suicidal behavior has been increasing. Currently, even with high quality treatment, there is a high incidence of early suicidal events in outpatient care.

Adolescent suicidal behavior is common, with more than 2,000,000 adolescents presenting to emergency departments (EDs) each year with suicidal behavior. Nearly 7% of adolescents in any one year make a suicide attempt, and an equal number have clinically significant suicidal ideation with a plan (Lewinsohn, Rohde, & Seeley, 1996). Suicide is the 2nd leading cause of death among 12-17 year olds, and suicidal behavior is associated with functional impairment and significant costs to the health care system, other service systems, and families (Centers for Disease Control and Prevention, 2010; Curtin et al., 2016; Florence, Haegerich, Simon, Zhou, & Luo, 2015; Shepard, Gurewich, Lwin, Reed, & Silverman, 2015). Short-term costs include costs of medical care for youth with suicide attempts, lost productivity for youth who die, and costs to families such as lost productivity for family members caring for youth in crisis. While Healthy People 2020 has as its objective to reduce suicide and suicide attempts in adolescents, trends for more than a decade have shown an increase in teen suicide (Curtin et al., 2016).

Focus early in treatment. In clinical populations, one of the times of greatest risk for recurrent suicidal behavior and completed suicide is during transition of care (transition between inpatient and outpatient care; prior to or at the onset of outpatient care), and quality improvements in this window of time have been shown to decrease the suicide rate in adults (Appleby, Dennehy, et al., 1999; Appleby, Shaw, et al., 1999; While, et al., 2012). The window of greatest risk is in the 1-4 weeks after the initial suicide attempt, with 25-50% of all suicidal events (defined as a suicide attempt or an increase in suicidal ideation)

occurred within the first 4 weeks of treatment (Brent, Greenhill, et al., 2009; Vitiello, Silva et al., 2009; Wilkinson, Kelvin, Roberts, Dubicka, & Goodyer, 2011). Thus, providing a brief, targeted intervention prior to discharge that protects against acting on suicidal urges in early outpatient treatment could make a substantial contribution towards reducing the incidence of youth suicidal behavior.

Early-onset of suicide event, even in high-quality treatment of suicidal ideation. In clinical studies of adolescents with treatment resistant depression, in which participants received close monitoring and either medication management alone, or in combination with CBT, the rate of suicidal events was 28% in the first 12 weeks of treatment, with a median time to event of 3 weeks (Brent, Emslie, et al., 2009). In an open trial of a CBT intervention especially designed to reduce suicide attempts in depressed adolescent suicide attempters, 40% of all suicidal events took place within the first 3 weeks of treatment (Brent, Greenhill, et al., 2009). Moreover, one of the most potent predictors of an eventual attempt or suicidal event is high baseline suicidal ideation (Brent, Emslie, et al., 2009; Brent, Greenhill, et al., 2009; Vitiello, Silva, et al., 2009; Wilkinson et al., 2011). In community samples, 56% and 29% of adolescents with suicidal ideation with or without a plan, respectively, will make a suicide attempt within a year of assessment (Nock et al., 2013).

**Safety Planning.** The safety plan, a structured set of coping strategies that a suicidal individual can deploy to de-escalate suicidal risk in the face of suicidal urges or identified precursors thereof (e.g., anger, sadness) is considered best practice for the management of high risk patients. The plan, developed with a mental health clinician, consists of: (1) activities the suicidal individual can do independently or alone (e.g. distraction, deep breathing); (2) reaching out to supportive individuals; and (3) finally, seeking clinical attention (Samra & Bilsker, 2007; Stanley et al., 2009). A safety plan is developed in the context of treatment, in which a chain analysis of the events leading up to the suicidal episode is conducted, a more comprehensive treatment plan to reduce suicidal risk is developed, and motivational techniques are deployed to enhance use of the safety plan and follow-up with treatment.

While safety plans have become a mainstay of clinical care, methods to facilitate their implementation have not yet been critically evaluated, nor has the efficacy of safety plans in preventing future suicidal acts been carefully evaluated (Knox et al., 2012). In order for a youth in crisis to deploy his or her safety plan, the plan has to be accessible. Youth at high risk for suicide who are being treated for suicidality may have a written safety plan as part of their treatment; however, this plan may not always be accessible when they experience suicidal urges. Therefore, identifying an alternative mechanism to increase accessibility and utility of safety plans could be quite helpful.

A precursor of the modern safety plan was developed by Rotheram-Borus and Bradley (1991), in which youth in a shelter for homeless runaways were taught a 5-step program for coping with suicidal ideation: 1. Identify 3 positive compliments about self; 2. Identify 3 people to go to for support; 3. Learn how to monitor and regulate emotion using an “emotion thermometer” in order to cope with suicidal urges; 4. Develop a concrete alternative to acting on suicidal impulses; and 5. Make a commitment to refrain from engaging in suicidal behavior. The number of suicide attempts in these shelters prior to implementation of the program was 9 in the previous 3 months, compared to 2 in the subsequent 18 months, which, when corrected for the period of observation, is a 27-fold decrease in the incidence of suicide attempts (assuming a similar number of youth in both conditions). This suggests that a brief intervention using emotion regulation techniques and mobilization of social support to cope with suicidal urges can be effective in reducing the probability that an adolescent will act on his or her suicidal ideation. However, to our knowledge, other than this study, the efficacy of safety planning has never been critically evaluated, particularly in adolescents.

Utilizing technology for improving distress tolerance and safety planning. Approximately 73% of American youth have or have access to smart phones (Lenhart, 2015). Close to 80% of homes have internet access, and for 21% of teens (up to 44% of minority teens), a cell phone is the teen’s sole means of access to the

Internet (Lenhart, 2010). Consequently, use of technology in this population to extend treatment is logical and timely. There are no empirically tested phone apps for safety planning, especially for teens, but there is a randomized trial to evaluate a safety planning app in adults currently underway (Andreasson et al., 2017). While there are cell phone applications related to safety planning in adults with suicidal behavior (Emory News, 2013; De la Torre, Castillo, Arambarri, Lopez-Coronado, & Franco, 2017; Larsen, Nicholas, & Christensen, 2016; Stanley & Brown, 2012;). We propose to supplement standard care by evaluating a safety plan smartphone application (which has been developed with promising outcomes; Kennard et al., 2015) that teens can easily access to provide tools to cope with suicidal urges and preserve safety.

## **Study Objectives**

The purpose of the study is to test the efficacy of BRITEPath intervention components developed in the open feasibility trial in STUDY18120080. This Phase 2 BRITEPath study will test 100 participant dyads (age 12-26; adolescent & parent or just young adult) in a 2:1 allocation toward intervention compared to Treatment As Usual (TAU) randomized controlled trial.

### **Aim 2 (Phase 2, Deployment)**

RE-AIM Framework. We will evaluate uptake of BRITEPath by clinical sites utilizing the RE-AIM framework and determine implementation outcomes as follows: Reach: Compare demographic and clinical characteristics of those patients who do versus do not (opt-out) get BRITEPath in practice for sample representativeness. Efficacy: Measure the percentage of patients for whom clinically significant reductions in depressive symptoms and suicidality as well marked improvements in functioning are obtained.

Adoption: The percentage and characteristics of clinicians who participate in the BRITEPath study.

Implementation: The percentage and characteristics of clinicians who follow through with BRITEPath use procedures (examining different components of app use). Maintenance: Extent BRITEPath is utilized and predictors of utilization after research support has been withdrawn. Please see Methods Core for full list of measures that will be collected and mapping of assessment measures onto RE-AIM framework.

Method: We will test efficacy of BRITEPath (Study 3) using 2:1 allocation randomized controlled trial of intervention compared to Treatment As Usual (n = 100). Qualitative study findings by [name] and within the Methods Core will inform iterative updates to BRITEPath platform to optimize practice implementation. The Methods Core details additional information regarding this design approach.

Feasibility: All sites will have a trained mental health specialist on site. Assessments: In both treatment conditions, patients will rate depressive symptoms and functioning as well as the extent of distress and intensity of suicidal and self-harm urges using an emotional thermometer on a 0-10 Likert scale prior to and after each MH visit in both BRITEPath and TAU. Follow-up assessments will be Call Center supported by our Methods Core blind to intervention. Primary outcomes are changes in suicide ideation and NSSI; secondary outcomes include changes in impairment and service use. Assessments will occur at 4 & 12 weeks post intake, and will cover self-reported depression (PHQ-9), suicidal ideation and behavior and NSSI (C-SSRS), imminent suicide attempt risk (adaptive suicide risk screen), impairment (parent report on 5- item scale from SDQ), firearms access and storage, and service use (CASA and EHR).

## **Study Design & Method**

This study is a randomized controlled trial with a 2:1 allocation of the BRITEPath intervention to Treatment As Usual comparator

### **Overview of the BRITEPath intervention**

There are three components of the BRITEPath intervention, each of which will be described: 1) BRITE, 2) GUIDE2BRITE and 3) BRITEBoard. All participants assigned to the intervention components will receive each of these 3 components.

#### **BRITE**

BRITE is a tool for self-monitoring and self-management that is not targeting any specific diagnosis or medical condition. BRITE includes monitoring of distress on a daily basis paired with content targeting skill targeting emotion regulation, distress tolerance, social support, and reasons for living. Content will take the form of clinician-recommended videos, photos, and websites, as well as personalized content that has salience to the adolescent that they may add onto their app. In this way, the app is customizable to uniquely meet the adolescents' needs and preferences. Adolescents will be encouraged to use the skills on the app on a daily basis. Additionally, the BRITE app will include an electronic version of a safety plan that will be developed in collaboration with the youth's therapist. Safety plans, which contain coping strategies, social supports, and crisis contacts are used as a standard of care in the treatment of suicidal youth. Finally, on each screen of the app, there is a link to crisis contacts that will be programmed onto the app with the assistance of their therapist.

#### **GUIDE2BRITE**

Embedded mental health providers, who will treat youth who have access to the BRITE app, will use GUIDE2BRITE to facilitate the process of orienting youth to the app. GUIDE2BRITE will be an interactive website that leads the clinician through the process of developing a safety plan and identifying appropriate content for the BRITE app with their adolescent patient. During this process, providers will orient patients on the purpose and function of the app, demonstrating and practicing skills they will use as part of the app-based intervention. Guide2BRITE supports clinicians in the delivery of an intervention designed to: (a) identify likely triggers of suicidal and self-harm urges; assess lethality and restricting access to means; (b) teach skills via modeling and role-play to cope with suicidal and self-harm urges and (c) identify professional resources to access in a crisis should others means of coping fail. A mock-up that shows the integration between BRITE and GUIDE2BRITE is provided within question 2.

#### **BRITEBOARD**

BRITEBOARD is a web-based portal that tracks participants use of the app, e.g. tracking distress ratings and times in which they added/removed content, as well as changes in patient outcomes over time, e.g. depression ratings collected as part of the study. In order to facilitate effective communication within the participant's clinical team, information on this portal will be shared among the adolescents' providers within their CCP practice, including the embedded therapist, their primary care provider, and other providers within the office that are designated as part of the adolescents' care team.

#### **Treatment As Usual**

Those who are assigned to the treatment as usual group will receive standard care within study practices. Among MH clinicians in primary care and mental health organizations, standard care involves developing a paper-based safety plan with depressed youth and youth who are at suicidal risk.

## **Eligibility Criteria**

### **Inclusion Criteria:**

- Youth aged 12-26 yo
- Own a device (e.g. smartphone, ipod, ipad, tablet) with capability to download BRITE app
- Biological or adoptive parent is willing to provide informed consent for teen to participate
- Youth speaks and understands English
- Patient is seeing mental health clinician for a mood or behavior problem at a study recruitment site

### **Exclusion Criteria:**

- Non English speaking
- No parent willing to provide informed consent
- No cell phone capability of downloading BRITE app

For the following symptoms-youth has to be prohibited by the diagnosis or symptoms to the point they would not understand or be able to participate in the study:

- Current or past history of mania or psychosis symptoms
- Evidence of an intellectual or developmental disorder (IDD)
- Life threatening medical condition that requires immediate treatment (included emergent suicidality, homicidality, abuse/neglect, or other mental or physical condition)
- Other cognitive or medical condition preventing youth from understanding study and/or participating.

## Statistical Considerations

Due to the pilot nature of the Center's research studies, sample size and power considerations center around the precision of confidence interval (CI) width estimation for feasibility outcomes. In Phase 1 in previous ETUDES studies (Development), a sample size of 50 afforded 95% CI width of no more than 0.28.

In the Deployment (phase of this current protocol-Phase 2) and future phases, a sample size of 100 (assuming 80% retention) affords us a 95% CI width of 0.09 0.13 for BRITEPATH study (study 3).

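### The Phase 2 CI width of 0.09 to 0.13 does not hold on the basis that reproduces the Phase 1 figure beside it; on that basis 80 retained give at most 0.22

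*Combined protocol and SAP*

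**What the plan says.** The Statistical Considerations section bases the sample size on the "precision of confidence interval (CI) width estimation for feasibility outcomes". It then gives two figures in consecutive sentences:

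- For Phase 1: "a sample size of 50 afforded 95% CI width of no more than 0.28".
- For Phase 2, the present trial: "a sample size of 100 (assuming 80% retention) affords us a 95% CI width of 0.09 0.13".

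The separator between 0.09 and 0.13 may have been lost when the PDF was read. It is taken as a range, and its absence is not counted against the plan.

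For the Phase 2 figure the section gives no expected proportion, interval method, denominator (pooled or one arm; dyads or individuals) or indication of full or half width. Under Study Objectives, the trial "will test 100 participant dyads (age 12-26; adolescent & parent or just young adult". The same sentence sets randomisation at two to BRITEPath for each one to TAU. Under Aim 2, the plan adds that "The Methods Core details additional information regarding this design approach". That source is not among the documents.

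**The concern.** The two sentences use the same word, width, with no sign that its meaning changes. Going from 50 participants to 80 retained should narrow an interval by a factor of the square root of 50/80, or about 21%. The stated figures fall from 0.28 to between 0.13 and 0.09, which is 54% to 68%. Sample size alone cannot account for that.

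This is the only numerical support for enrolling 100. A reader who carries the Phase 1 meaning forward will expect feasibility rates to be estimated within intervals of total length 0.09 to 0.13. With 80 retained, the interval can be as long as 0.22 unless the rate is very high or very low.

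**Working it through.** **Inputs.** From Statistical Considerations: 95% confidence, 50 participants and at most 0.28 (Phase 1), 100 enrolled and 80% retention (Phase 2), so 100 × 0.80 = 80 retained. From Study Objectives: 2:1 allocation, so with equal retention 80 × 2/3 ≈ 53 in BRITEPath and 80 × 1/3 ≈ 27 in TAU. Assumptions: each feasibility outcome is a single proportion p, and the interval is two-sided and Wald.

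**Formula.** Full width W = 2 × 1.96 × √(p(1−p)/n). The half-width is W/2.

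**Step 1: reproduce Phase 1.** With n = 50 and p = 0.5, W = 3.92 × √(0.25/50) = 0.277, which rounds to 0.28. The largest half-width at n = 50 is 0.139. The Phase 1 figure is therefore a full width at the worst-case proportion.

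**Step 2: Phase 2 on the same basis.**

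- n = 80: 3.92 × √(0.25/80) = 0.219. Scaling the plan's own figure agrees: 0.28 × √(50/80) = 0.221.
- n = 100, ignoring attrition: 3.92 × √(0.25/100) = 0.196.
- Other methods at n = 80, p = 0.5: Wilson 0.214, Clopper-Pearson 0.228.
- Worst-case full widths of 0.13 and 0.09 need (1.96/0.13)² = 227.3 and (1.96/0.09)² = 474.3, so 228 and 475 analysed.

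**Step 3: proportions that give the stated range as a full width at n = 80.** Solve p(1−p) = 80 × (W/3.92)².

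- W = 0.13: p(1−p) = 0.0880, so p = 0.902 or 0.098.
- W = 0.09: p(1−p) = 0.0422, so p = 0.956 or 0.044.

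For comparison, full widths at n = 80 are 0.175 at p = 0.8, 0.131 at p = 0.9 and 0.096 at p = 0.95. The pilot's 45.5% safety-plan access (Scientific Background) gives 0.218.

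**Step 4: other routes to the range.**

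- Full width on all 100 with no attrition: p of about 0.87 to 0.94, or the mirror range.
- Half-width on the whole sample: the maximum is 0.110 at n = 80 and 0.098 at n = 100, so 0.13 is out of reach.
- Half-width in the BRITEPath arm at p = 0.5: about 53 retained dyads give 1.96 × √(0.25/53) = 0.135 (0.134 at the unrounded 53.3). Counting both members of each dyad gives 2 × 53.3 ≈ 107 individuals and 1.96 × √(0.25/107) = 0.0947. These round to about 0.13 and 0.09, although 106 individuals would give 0.0952.
- Full width on 160 individuals (both members of 80 dyads): p of about 0.77 to 0.91, or 0.09 to 0.23.

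**Step 5: by arm on the Phase 1 basis.** BRITEPath: 3.92 × √(0.25/53) = 0.269. TAU: 3.92 × √(0.25/27) = 0.377.

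**The case against.** The strongest defence is that both ends of the range can be reached at p = 0.5 from counts the plan does state. As half-widths in the BRITEPath arm, about 53 retained dyads give about 0.13, and the same dyads counted as about 107 individuals give about 0.09. Because young adults may enter alone, the number of individuals lies somewhere between, so a range would be natural. This stands as a possible origin. It does not rescue the sentence, for two reasons. It turns width into half-width directly after a full width, and it ignores the pairing of youth and parent. Neither choice is stated.

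It is also fair that Phase 1 is worded as an upper bound and Phase 2 is not. Since 0.09 to 0.13 lies below 0.22, the sentences do not strictly contradict each other. High feasibility rates of 0.90 to 0.96 would make the figure correct as a full width, and the Methods Core material may state such an assumption.

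A reader might go further and infer a plain arithmetic mistake, or that the precision is wrong by a factor of 1.7 to 2.4 (0.22/0.13 and 0.22/0.09). The documents support neither. The range is attainable under unstated assumptions, and those ratios compare a worst-case maximum with a figure not offered as a maximum, so they do not measure an error.

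**Conclusion.** The point holds in a limited form. Taken with the meaning of width that reproduces the Phase 1 figure, the Phase 2 statement promises more precision than 80 retained participants deliver, except at proportions of about 0.90 to 0.96 or 0.04 to 0.10. At 80% or 20% the full width is 0.18, and in the worst case it is 0.22. The basis that would justify 0.09 to 0.13 is missing from the documents available.

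This rests on reading the two values as a range, on feasibility outcomes being single proportions, and on Wald intervals; Wilson and Clopper-Pearson change the worst case only to 0.214 and 0.228. Confidence is medium, because an unseen source may supply the missing assumption. It should be fixed, as no other figure supports the sample size. It does not show that 100 is too few for the trial.

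**What to change.** Restate the Phase 2 precision on the Phase 1 basis, for example: with 100 enrolled and 80% retained, the full 95% confidence interval width for a feasibility proportion is at most 0.22 (0.18 at 80% or 20%; 0.13 at 90% or 10%); by arm, with equal retention, it is at most about 0.27 in BRITEPath (about 53) and 0.38 in TAU (about 27).

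If 0.09 to 0.13 is kept, state beside it:

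- whether it is a full or half width;
- the assumed proportion or proportions, with a reason for them;
- the denominator: pooled or one arm, dyads or individuals. If individuals are counted, allow for pairing within dyads.

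The cost is a less favourable stated precision, unless the assumptions behind the present figure are given and justified. No extra participants are needed.

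### The planned CI width shows no allowance for patients sharing clinicians and sites, and it cannot describe the two outcomes counted in clinicians

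*Combined protocol and SAP*

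**What the plan says.** Statistical Considerations gives one basis for the sample size: "sample size and power considerations center around the precision of confidence interval (CI) width estimation for feasibility outcomes". For Phase 1 it reports that "a sample size of 50 afforded 95% CI width of no more than 0.28". For this study it says that "a sample size of 100 (assuming 80% retention) affords us a 95% CI width", printed as 0.09 0.13, which I read as a range from 0.09 to 0.13. The sentence adjusts for 80% retention and for nothing else. It does not name the outcome, the expected proportion, the interval method, full or half width, the unit of analysis, the number of clinicians or sites, or an intracluster correlation.

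Other sections show the structure of the data. Eligibility requires that each patient is seeing a mental health clinician at a recruitment site. Aim 2 refers to sites in the plural. GUIDE2BRITE describes "Embedded mental health providers, who will treat youth who have access to the BRITE app" as the people who orient patients to the app and build the safety plan and app content with them.

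Aim 2 also defines two outcomes in clinicians. Adoption is "The percentage and characteristics of clinicians who participate in the BRITEPath study". Implementation is "The percentage and characteristics of clinicians who follow through with BRITEPath use procedures". No number of clinicians and no precision is given for either.

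**The concern.** Set-up and early use of the app pass through the clinician, so patients of the same clinician are likely to resemble one another on feasibility outcomes. Patients within a site may do so too. A width worked out for independent patients is then more favourable than the data can deliver. For percentages of clinicians the problem is simpler: the denominator is clinicians, so the number of patients says nothing about their precision.

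This matters because CI width is the only justification offered for enrolling 100. The supplied text has no power calculation, effect size or analysis model to fall back on.

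**Working it through.** **Inputs from the documents.** 100 enrolled and 80% retention, so 100 × 0.80 = 80 analysed; stated width 0.09 to 0.13; Phase 1 benchmark of at most 0.28 with n = 50 (all from Statistical Considerations).

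**Assumed, because the documents do not say.** 10, 20 or 30 clinicians of equal caseload; ICC of 0.01, 0.05 or 0.10.

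**Step 1: find the convention.** The full width of a normal-approximation 95% interval for one proportion is 2 × 1.96 × √(p(1−p)/n). With n = 50 and p = 0.5 this is 3.92 × √(0.25/50) = 0.277, which reproduces the Phase 1 figure as a worst-case width for independent patients.

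**Step 2: apply it to this study.** With n = 80 and p = 0.5, 3.92 × √(0.25/80) = 0.219. With all 100 it is 0.196. Neither is 0.09 to 0.13. Solving p(1−p) = 80 × (width/3.92)²:

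- width 0.13: p(1−p) = 0.088, so p = 0.903;
- width 0.09: p(1−p) = 0.042, so p = 0.956.

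The complements (0.097 and 0.044) serve equally. Read as full widths, the stated figures therefore need a proportion of about 0.90 to 0.96, or its complement. None is stated.

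**Step 3: clustering of patients.** Design effect = 1 + (m−1) × ICC, with m = 80 divided by the number of clinicians. The width is multiplied by the square root of the design effect.

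| Clinicians | m | ICC 0.01 | ICC 0.05 | ICC 0.10 |
|---|---|---|---|---|
| 10 | 8 | 1.07, +3% | 1.35, +16% | 1.70, +30% |
| 20 | 4 | 1.03, +1% | 1.15, +7% | 1.30, +14% |
| 30 | 2.7 | 1.02, +1% | 1.08, +4% | 1.17, +8% |

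Cells show the design effect and the growth in width. In the largest case (10 clinicians, ICC 0.10) the multiplier is √1.70 = 1.304, so 0.09 to 0.13 becomes 0.12 to 0.17, and 0.219 becomes 0.286. Correlation within sites beyond that within clinicians is not included.

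**Step 4: clinician-level percentages.** The same formula with k clinicians in place of n:

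| Clinicians | p = 0.5 | p = 0.9 |
|---|---|---|
| 10 | 0.62 | 0.37 |
| 20 | 0.44 | 0.26 |
| 30 | 0.36 | 0.21 |

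The normal approximation is rough at these counts. Wilson intervals give 0.53, 0.40 and 0.34 at p = 0.5, and 0.39, 0.27 and 0.22 at p = 0.9, which leads to the same conclusion. A width of 0.13 at p = 0.9 would need (3.92/0.13)² × 0.09 = 82 clinicians.

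**The case against.** The strongest reply is that independence is inferred. The stated width cannot be reproduced from stated inputs. If 0.09 and 0.13 are half-widths, 0.13 is more than 80 independent patients can give (at most 0.110 at p = 0.5). It would fit a design effect of (0.13/0.110)² ≈ 1.4, or the roughly 53 retained patients in the BRITEPath arm (100 × 2/3 × 0.80). This stands. The Phase 1 match makes independence likely but does not prove it.

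The section never says that its feasibility outcomes include Adoption and Implementation, which Aim 2 calls implementation outcomes. This also stands: a reader might infer that a width of 0.13 was promised for clinicians, and the text does not go that far. What remains is that two named outcomes have no precision statement, and the only one in the plan cannot serve them.

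Aim 2 refers to a Methods Core, not supplied, for more on measures and design. Clinician numbers or a clustering allowance may be there. If so, the sizing paragraph should cite them.

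A reader might also infer a large effect, such as widths 40% greater and coverage of 84%. That takes 20 patients per clinician at an ICC of 0.05, so only 80/20 = 4 clinicians (5 if all 100 are counted). The documents give no such number. For outcomes that arise only in the BRITEPath arm the caseloads are smaller still: 53 patients over 10, 20 or 30 clinicians at an ICC of 0.05 give growth of about 10%, 4% and 2%.

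Finally, a reader might infer that the comparison between arms needs a clinician effect. The widths examined here are for single proportions. The effect of clustering on the arm contrast depends on whether the same clinicians treat both arms, which the text does not say.

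**Conclusion.** The point holds in a limited form. The sizing paragraph shows no allowance for visible nesting, and its width cannot describe the two clinician percentages. The second part needs no assumption about the ICC; only its size depends on the unknown number of clinicians. At every count tried, from 10 to 30, the clinician-level width is well above 0.13, even at a proportion of 0.9.

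For patient-level outcomes, clustering probably adds a modest amount: 4% to 16% at an ICC of 0.05, and about 1% to 30% over the whole assumed range. The unstated proportion matters more. Under the Phase 1 convention 80 patients give 0.22, and that gap exists before any clustering. The documents do not support saying that the stated width is wrong by a known factor, or that the final intervals will be too narrow, because neither the calculation nor the interval method is given.

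**What to change.** In Statistical Considerations:

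1. Limit the stated width to patient-level outcomes. Restate it for the retained number, naming the outcome, expected proportion, interval method, full or half width, and an assumed design effect with its ICC and patients per clinician.
2. Give a separate width for Adoption and for Implementation from the planned number of clinicians in each denominator, and state the number of sites.
3. Specify clinician-clustered, small-sample-corrected standard errors for the intervals on patient-level feasibility proportions.
4. If the Methods Core already covers any of this, cite it here.

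The cost is a change of wording, slightly wider stated intervals, and a clinician identifier kept in the analysis data. The documents do not say whether that identifier is held for both arms, so this should be confirmed. No extra patients are needed. No change to the arm comparison is asked for on this ground.
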